5.1.3 Derived variables

Table 1. Derived variables of SHR-1210

Variable	SHR-1210
Protocol-Specified Method of Administration	200 mg/dose, intravenous drip (no less than 20 min and no more than 60 min) on Day 1 of each 3-week cycle.
Duration of Drug Exposure (Month)	(Actual date of last dose – actual date of first dose + 21)/30.4375
Drug Exposure (mg)	The total administered dose of SHR-1210 in the subject
Actual Dose Intensity (mg/3 weeks)	Drug exposure/[duration of drug exposure (month) \times 30.4375/21]
Relative Dose Intensity (%)	100 \times actual dose intensity (mg/3 weeks)/200 (mg/3 weeks)

Table 2. Derived variables of apatinib

Variable	Apatinib
Protocol-Specified Method of Administration	Administered orally at 500 mg/day once daily. Each cycle contains 3 weeks.
Duration of Drug Exposure (Month)	(Actual date of last dose – actual date of first dose + 1)/30.4375
Drug Exposure (mg)	The total administered dose of apatinib in the subject
Intended Dose Intensity (mg/day)	500
Actual Dose Intensity (mg/day)	Drug exposure (mg)/[duration of drug exposure (month) \times 30.4375]
Relative Dose Intensity (%)	100 \times actual dose intensity (mg/day)/500

Table 3. Derived variables of doxorubicin

Variable	Doxorubicin
Protocol-Specified Method of Administration	Administered via intravenous drip infusion at 60 mg/m ² within 2 h on Day 1 of each 3-week cycle.
Duration of Drug Exposure (Month)	(Actual date of last dose – actual date of first dose + 21)/30.4375
Drug Exposure (mg/m ²)	Subject's actual cumulative dose (mg)/body surface area ⁽¹⁾
Intended Dose (mg/m ²)	(Actual date of last dose – actual date of first dose + 21) \times 60 mg/m ² /21
Relative Dose Intensity (%)	100 \times drug exposure (mg/m ²)/scheduled dose (mg/m ²)

Table 4. Derived variables of ifosfamide

Variable	Ifosfamide	
Protocol-Specified Method of Administration	Combination with doxorubicin: Ifosfamide 2 g/m ² /d on D1-D4, intravenous drip infusion within 4-6 h, in 3-week cycles (i.e., the total dose per cycle shall be 8 g/m ²).	Ifosfamide monotherapy: 2 g/m ² /d on D1-D5, intravenous drip infusion within 4-6 h, in 3-week cycles (i.e., the total dose per cycle shall be 10 g/m ²).
Duration of Drug Exposure (Month)	(Actual date of last dose – actual date of first dose + 21)/30.4375	
Drug Exposure (g/m ²)	Actual cumulative dose/body surface area ⁽¹⁾	
Intended Dose (g/m ²)	[(Date of last dose of doxorubicin – date of first dose of doxorubicin + 21)/21] × 8 g/m ² + [CEIL × (date of last dose of ifosfamide – date of last dose of doxorubicin – 4)/21] × 10 g/m ²	
Relative Dose Intensity (%)	100 × drug exposure (g/m ²)/intended dose (g/m ²)	

(1) The body surface area is calculated as: body surface area (m²) = 0.0061 × height (cm) + 0.0128 × weight (kg) – 0.1529. The body weight at baseline should be used.

*CEIL: round up

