10.1.5 Administration of study drugs

SHR-1210

Administered via intravenous drip infusion at 200 mg/dose (not less than 20 min and not more than 60 min) on day 1 of each 3-week cycle for a period of up to 2 years.

Apatinib Mesylate Tablets

Administered orally at 500 mg/day once daily with warm water at approximately half an hour after meals (administration time should be the same in each day whenever possible) in 3-week cycles.

Doxorubicin

Administered via intravenous drip infusion at 60 mg/m^2 within 2 h on day 1 of each 3-week cycle. Six cycles are recommended.

If a subject has received more than 450 mg/m^2 of anthracyclines, doxorubicin will no longer be used. Doxorubicin will also be discontinued if the subject experiences a decrease in LVEF from baseline by at least 5% to an absolute value of $< 55\%$ with symptoms of chronic heart failure, or a decrease in LVEF from baseline by at least 10% to an absolute value of $< 55\%$ without symptoms or signs.

If the subject has received anthracycline treatment before the study, refer to [Appendix 3. Dose Conversion of Anthracyclines](#) for the conversion. In the course of the study, if the remaining available dose of doxorubicin (450 mg/m^2 minus the cumulative dose used previously) is $\geq 51 \text{ mg/m}^2$ (i.e., 85% of the initial dose) in a certain cycle, then the doxorubicin + ifosfamide regimen is still used this time. If the remaining available dose of doxorubicin is less than 51 mg/m^2 , the ifosfamide monotherapy regimen is used directly.

The body surface area is calculated using the Stevenson's formula: body surface area (m^2) = $0.0061 \times \text{height} (\text{cm}) + 0.0128 \times \text{weight} (\text{kg}) - 0.1529$. The final dose should be 95-105% of the calculated dose.

Ifosfamide

Combination with doxorubicin: Ifosfamide $2 \text{ g/m}^2/\text{d}$ on D1-D4, intravenous drip infusion within 4-6 h, in 3-week cycles (i.e., the total dose per cycle shall be 8 g/m^2). Six cycles are recommended.

Ifosfamide monotherapy: $2 \text{ g/m}^2/\text{d}$ on D1-D5, intravenous drip infusion within 4-6 h, in 3-week cycles (i.e., the total dose per cycle shall be 10 g/m^2). Six cycles are recommended.

If the above infusion rate is not tolerated by the subject, the investigator may consider adjusting the ifosfamide infusion rate.

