5.5.1 Extent of exposure

See Section 5.1.3 for the specific defining rules of the derived variables of study drugs SHR-1210, apatinib, doxorubicin, and ifosfamide.

The drug exposure, duration of drug exposure, actual dose intensity, and relative dose intensity of apatinib and SHR-1210, as well as the duration of drug exposure and drug exposure of doxorubicin and ifosfamide are described using the mean, standard deviation, maximum, minimum, and median.

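### The ifosfamide intended-dose formula in SAP Table 4 rounds the monotherapy phase up to whole cycles and cannot be computed for subjects who start on monotherapy

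*SAP*

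**What the plan says.** SAP 5.1.3, Table 4, defines ifosfamide relative dose intensity as "100 × drug exposure" divided by intended dose, both in g/m². Intended dose is the sum of two terms.

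- Combination term: "Date of last dose of doxorubicin – date of first dose of doxorubicin + 21", divided by 21 and multiplied by 8 g/m². It is not rounded.
- Monotherapy term: "date of last dose of ifosfamide – date of last dose of doxorubicin – 4", divided by 21, with CEIL written in front, and multiplied by 10 g/m². The interval thus ends at the "date of last dose of ifosfamide". A footnote explains CEIL as rounding up.

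The multipliers match the regimens in the same table. In combination (D1-D4) "the total dose per cycle shall be 8" g/m²; as monotherapy (D1-D5) "the total dose per cycle shall be 10" g/m². The doxorubicin intended dose in Table 3 is pro-rata, with no rounding.

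Protocol 10.1.5 says that when less than 51 mg/m² of the 450 mg/m² doxorubicin allowance remains, "the ifosfamide monotherapy regimen is used directly". Protocol 11.2.2 lists ifosfamide monotherapy as a possible C1D1 treatment in the control group.

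SAP 5.5.1 lists dose intensity and relative dose intensity as summaries for apatinib and SHR-1210, "as well as the duration of drug exposure and drug exposure of doxorubicin and ifosfamide are described". It does not list relative dose intensity for the two control drugs.

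**The concern.** The two halves of one denominator follow different rules. The combination half grows smoothly with elapsed time. The monotherapy half moves in steps of a whole cycle, and a subject exactly on schedule sits at the edge of a step. Rounding up can only raise the intended dose, so any error lowers ifosfamide relative dose intensity. Both halves also need doxorubicin dates, which a subject put directly on monotherapy does not have. SAP 5.1.4 (missing data) gives no rule for that case.

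At stake is a descriptive measure of how fully the control chemotherapy was delivered. Readers of an open-label comparison with chemotherapy will want that measure, and they will want it computed alike in both arms.

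**Working it through.** **Inputs.** Cycle length 21 days; 8 g/m² per combination cycle and 10 g/m² per monotherapy cycle (SAP Table 4); full-dose monotherapy on D1-D5 (SAP Table 4); doxorubicin 60 mg/m² per cycle, allowance 450 mg/m², threshold 51 mg/m² (Protocol 10.1.5). CEIL is taken to round up the whole ratio, days/21. The SAP gives no worked example to reproduce, so the first check is whether the formula returns the planned dose for a subject on schedule.

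**On schedule.** With c combination cycles, first and last doxorubicin are 21(c − 1) days apart, so the first term is 8c. With m monotherapy cycles, the last ifosfamide dose falls 21m + 4 days after the last doxorubicin dose. The second term is CEIL(21m/21) × 10 = 10m. With no monotherapy, the last ifosfamide dose is 3 days after doxorubicin, and CEIL(−1/21) = 0. Intended dose equals planned dose, 8c + 10m, and relative dose intensity is 100%.

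**One day late after the last doxorubicin dose, all doses given in full.** The second term becomes CEIL((21m + 1)/21) × 10 = 10(m + 1). Pro-rata it would be 10m + 10/21 = 10m + 0.48.

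| Cycles (combination + monotherapy) | Given, g/m² | Intended, rounded up | Relative dose intensity | Intended, pro-rata | Relative dose intensity |
|---|---|---|---|---|---|
| 7 + 1 | 66 | 76 | 86.8% | 66.48 | 99.3% |
| 7 + 2 | 76 | 86 | 88.4% | 76.48 | 99.4% |
| 7 + 3 | 86 | 96 | 89.6% | 86.48 | 99.4% |
| 6 + 1 | 58 | 68 | 85.3% | 58.48 | 99.2% |

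**Size by length of delay.** For a cumulative delay of d days, the excess over pro-rata is 10 × (CEIL(d/21) − d/21) g/m²: 9.52 at 1 day, 0.48 at 20 days, 0 at 21 days. Day 22 starts a second step: for 7 + 3 cycles, 86/106 = 81.1% against 86/96.48 = 89.1% pro-rata. At 42 days the excess is again 0.

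**Which switch is typical.** An anthracycline-naive subject on full dose has 450 − 6 × 60 = 90 mg/m² left after six cycles, so cycle 7 is still combination. After seven, 450 − 420 = 30, below 51, so the switch comes at cycle 8. By cumulative dose, 6 + 1 needs more than 39 mg/m² of doxorubicin-equivalent before entry (450 − 360 − 51 = 39) and at most 99 mg/m² (450 − 300 − 51 = 99).

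**What does not move.** Six combination cycles with one cycle a day late: (106 + 21)/21 × 8 = 48.38 g/m², and 48/48.38 = 99.2%, which is correct pro-rata behaviour. Doxorubicin relative dose intensity has no CEIL. One narrow exception exists among combination-only subjects. If the final ifosfamide dose slips two days within the last cycle, CEIL(1/21) = 1 and a monotherapy cycle that was never planned is added (48/58 = 82.8%). A one-day slip gives CEIL(0) = 0.

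**Monotherapy starters.** Prior exposure above 450 − 51 = 399 mg/m² doxorubicin-equivalent sends a control subject straight to monotherapy. The first and last doxorubicin dates do not exist, so neither term can be computed.

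**The case against.** The strongest reply is that little depends on this variable. SAP 5.5.1 plans only exposure and duration for the control drugs, and neither uses the formula. No efficacy analysis uses it either. The affected group is a subset: for a naive full-dose subject, cycle 8 starts on day 148 at the earliest (7 × 21 = 147 days, 147/30.4375 = 4.8 months), beyond the six recommended cycles and the assumed control median PFS of 4.5 months. The one-day figures are the largest gap, which shrinks to nothing at 21 days. Reduced-dose monotherapy, listed in Protocol Table 8 as D1-D4, has a day of slack. All of this stands, and it keeps the point minor.

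The notation is also open to another reading, because CEIL is followed by a multiplication sign. If only the days are rounded, nothing is rounded and there is no step. That reading gives a combination-only subject a second term of −10/21 = −0.48 g/m² (six cycles: 48/47.52 = 101.0%), whereas the whole-ratio reading is exact on schedule. The whole-ratio reading is therefore the more likely one, but the text should not leave the choice to the programmer.

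Three stronger readings are tempting, and the documents do not support them. A reader might infer that any one-day delay adds a cycle; delays between combination cycles are pro-rated, and cumulative delays of 1 to 21 days add one cycle in total. A reader might infer that control-arm dose intensity is wrong as a whole; doxorubicin and on-schedule subjects are untouched. A reader might infer that the superiority result is exposed; nothing in the primary or secondary efficacy analysis uses this variable.

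**Conclusion.** The formula is wrong as written, with limited reach. For subjects who switch to D1-D5 monotherapy, a cumulative delay of 1 to 20 days after the last doxorubicin dose overstates the ifosfamide intended dose by 0.5 to 9.5 g/m² relative to the pro-rata rule used elsewhere in the SAP. At one day, a fully dosed subject reads about 85% to 90% in the cases tabulated instead of about 99%. For subjects who start on monotherapy the value is undefined.

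The size rests on reading CEIL as rounding the whole ratio and on full doses throughout. The number of subjects affected cannot be derived from the documents. The error biases or removes one descriptive exposure variable and does not threaten the trial's conclusions.

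**What to change.** In SAP Table 4, remove CEIL and use cycle day 1 dates.

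- Combination term: (last minus first combination day 1 + 21)/21 × 8; 0 if there was no combination cycle.
- Monotherapy term, switchers: (last monotherapy day 1 minus last combination day 1)/21 × 10.
- Monotherapy term, subjects who start on monotherapy: (last minus first monotherapy day 1 + 21)/21 × 10.
- Monotherapy term: 0 if no monotherapy was given.

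On schedule this returns 8c + 10m for switchers, 8c for combination-only subjects and 10m for monotherapy starters. For 6 + 1 cycles one day late it gives 58/58.48 = 99.2%.

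Two simpler repairs fail. Deleting CEIL alone leaves the −0.48 g/m² artefact in combination-only subjects. Measuring the switchers' monotherapy phase from its own first day 1 hides a delay at the switch: 6 + 1 cycles with a 42-day delay would read 58/58 = 100%, whereas the rule above gives 58/(48 + 63/21 × 10) = 58/78 = 74.4%.

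In SAP 5.5.1, add doxorubicin and ifosfamide relative dose intensity, already defined in Tables 3 and 4, so that both arms are reported alike.

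The cost is one table row, one derived variable and one line of text, made before database lock. No new data should be needed if dosing dates are recorded by cycle.

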5.1.4 Missing data

In this study, the missing data of the efficacy endpoints will not be treated specially, and the missing values will not be estimated in the safety evaluation.

If the specific date of death is missing, it will be imputed based on the first day of month of death.

If the specific day of the initial diagnosis is missing, it will be imputed with the first day of the month of initial diagnosis. If the month and day of the initial diagnosis are missing and the year of the initial diagnosis is before the year of the first dose, it will be imputed with 1 Jan. If the month and day of the initial diagnosis are missing and the year of the initial diagnosis is the same as the year of the first dose, it will be imputed with 1 Jan. If the date of the initial diagnosis is completely missing, it will not be imputed.

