12 EVALUATIONS

12.1 Efficacy Evaluation

In addition to the investigator's assessments of the tumor imaging results in this study, the sponsor will also collect all imaging results (except for the imaging results of the control group after crossover treatment), and use them for blinded independent review (all per RECIST v1.1). The specific procedures for independent review are described in the "Third-Party Independent Review Charter" for this study, written by the central imaging.

PFS: the time between the date of enrollment and the date of the first documented tumor progression (as per RECIST v1.1, regardless of whether treatment is continued), or death from any cause, whichever occurs first.

In addition, subjects in the investigational treatment group will continue the study treatment after progressive disease. The investigator will perform subsequent imaging assessments as per iRECIST (see Appendix 11; independent imaging evaluation is still carried out as per RECIST v1.1) for exploratory evaluation of PFS in the investigational treatment group as per iRECIST. PFS is defined as the period of time from the date of the subject's enrollment to the first iUPD that can be subsequently confirmed or the date of death due to any cause, whichever occurs first. The imaging evaluation criteria of the control group after crossover treatment are the same as those of the investigational treatment group, but no independent review of central imaging will be performed. The subjects after crossover will be analyzed based on the PFS data as per RECIST v1.1 and iRECIST.

OS: the time from the date of enrollment to the date of death from any cause. Subjects whose final status is "survived" are censored, and the date of censoring is the date of the last follow-up.

ORR: the proportion of treated subjects whose best overall response (BoR) is complete response (CR) or partial response (PR) as per RECIST1.1.

DCR: the proportion of treated subjects whose best overall response is complete response (CR), partial response (PR), or stable disease (SD) as per RECIST v1.1.

DoR: the period of time from the first documented tumor response (as per RECIST v1.1) to the first documented objective progression (as per RECIST v1.1) or death of any cause.

iORR: the proportion of treated subjects whose best overall response (BoR) is complete response (CR) or partial response (BOR) as per iRECIST v1.1.

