14.4.3 Secondary efficacy endpoint analysis

The analysis of secondary efficacy endpoints will be based on the FAS.

For the secondary endpoint PFS assessed by the investigator (as per RECIST v1.1), the analytical method will be the same as that of the primary endpoint mentioned above.

The secondary endpoint OS will be statistically described using the similar method for the primary endpoint. For DoR, the Kaplan-Meier method will be used to plot the survival curve and estimate the median DoR and its 95% confidence interval will be calculated (Brookmeyer-Crowley method).

For the objective response rate (ORR) and disease control rate (DCR), the rates in the two groups and their two-sided 95% CI (Clopper-Pearson method) will be estimated, and the inter-group difference of rates and its two-sided 95% CI will be calculated (CMH method).

Other endpoints will be statistically summarized in accordance with general principles.

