2.2.2 Secondary objectives

- To evaluate and compare the objective response rate (ORR) and disease control rate (DCR) of SHR-1210 combined with apatinib vs. doxorubicin combined with ifosfamide in the treatment of soft tissue sarcoma;
- To evaluate and compare the safety of SHR-1210 combined with apatinib vs. doxorubicin combined with ifosfamide in the treatment of soft tissue sarcoma;
- To evaluate and compare the quality of life scores in subjects with soft tissue sarcoma after treatment with SHR-1210 combined with apatinib vs. doxorubicin combined with ifosfamide.

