4 STUDY ENDPOINTS

4.1 Efficacy Endpoints

4.1.1 Primary efficacy endpoint

4.1.1.1 PFS assessed by the independent review committee as per RECIST v1.1

The primary endpoint of the study is the IRC-assessed PFS (as per RECIST v1.1).

PFS: the time between the date of randomization and the date on which the first tumor progression is documented (as per RECIST v1.1, regardless of whether treatment is continued), or death from any cause, whichever comes first.

The censoring rules for PFS are as follows:

- If there is no post-baseline objective tumor response evaluation or death, then the date of randomization will be censored.
- If there is no progressive disease (PD) or death as per RECIST v1.1, then the date of the last objective tumor response evaluation will be censored.
- If no imaging PD or death is recorded before the subject uses the new anti-tumor drug, the censoring date is the date of the last objective tumor response evaluation carried out before the subject uses the new anti-tumor drug.
- Before PD or death, if a subject has missed ≥ 2 consecutive scheduled imaging assessments, then the date of the last objective tumor response evaluation prior to the missing ones will be censored.

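### A missing day of death is set to the first of the month with no floor at the last date known alive, so a PFS death can be dated before a scan, a visit or randomization

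*SAP*

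**What the plan says.** SAP 5.1.4 opens with a general statement, "In this study, the missing data of the efficacy endpoints will not be treated specially", and then gives one rule for deaths: "If the specific date of death is missing, it will be imputed based on the first day of month of death". It attaches no exception, no floor at the last date known alive, no rule for a missing month and no sensitivity analysis. The same section gives the date of initial diagnosis a tiered rule. Protocol 14.4.4 has no rule for death dates.

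Death is an event in the primary endpoint. SAP 4.1.1.1 counts PFS from randomization to first progression "or death from any cause, whichever comes first". With no event, "then the date of the last objective tumor response evaluation will be censored". Two further censoring rules depend on date order. One begins "If no imaging PD or death is recorded before the subject uses the new anti-tumor drug"; the other censors a subject who missed two or more consecutive scheduled scans before progression or death.

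OS is defined in Protocol 12.1 ("OS: the time from the date of enrollment to the date of death from any cause") and analysed in Protocol 14.4.3 ("The secondary endpoint OS will be statistically described using the similar method for the primary endpoint"). The SAP has no OS objective, endpoint or analysis; its secondary efficacy objective in 2.2.2 reads "To evaluate and compare the objective response rate (ORR) and disease control rate (DCR") and names no time-to-event measure.

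**The concern.** The first of the month is the earliest date a death in that month can have, so any error runs one way. With no floor, the programmed date can also contradict data already held on the subject:

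- A subject scanned progression-free on the 12th who dies later that month, day unknown, gets a PFS event on the 1st. That is 11 days before a scan that found the subject alive and progression-free.
- A death in the month of randomization is dated before randomization unless randomization fell on the 1st, which gives a negative PFS time.
- A progression on the 12th followed by a death in the same month is overtaken by the imputed death on the 1st.
- A new anti-tumor drug started on the 10th, followed by a death in the same month, now appears to come after the death. A subject who should be censored then counts as an event. A death moved back by up to 30 days can likewise precede a second missed scan.

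At stake are the date, and occasionally the status, of some PFS observations. Someone would also have to make unplanned date decisions in an open-label trial.

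**Working it through.** **Plan's own figure.** The imputation rule carries no number. The design it sits in was checked first, because the simulation below uses it. With HR 0.64, one-sided 0.025, 90% power and 1:1 allocation (SAP 2.3), the fixed-design event count is 4 × (1.960 + 1.282)² / (ln 0.64)², which rounds up to 212. With one O'Brien-Fleming look at 143 of 214 events, the boundaries are 2.506 and 1.993, and 214 events give power 0.9006. Then 262 / 0.90 = 291.1, or 292 subjects. The plan's 214 and 292 reproduce and are not affected by this point.

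**Size of the shift.** A death on day d moves earlier by d − 1 days. In a month of length L the mean is (L − 1)/2, so 14.5 days for a 30-day month. Averaged over every calendar date from September 2018 for four years (Protocol section 20), the mean is 21,520 / 1,461 = 14.7 days, or 14.7 / 30.4375 = 0.48 month. The maximum is 30 days. The shift is nonzero for 96.7% of dates.

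**Impossible orders.** Assume the gap from last scan or contact to death is uniform over an interval of G days. Because the shift never exceeds 30 days and G is larger than that, the chance that the imputed date precedes the last scan or contact is (mean shift) / G:

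| Interval (SAP 2.1) | G | Chance, given a missing day |
|---|---|---|
| Scans every 2 cycles, first 16 cycles | 42 | 14.73 / 42 = 35% |
| Scans every 4 cycles thereafter | 84 | 14.73 / 84 = 18% |
| Survival contacts every 2 months | 61 | 14.73 / 61 = 24% |

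These are shares of deaths with a missing day, not of all deaths.

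**Trial-level effect.** The documents give neither the share of PFS events that are deaths nor the share of those with a missing day, so both are assumed: 10–30% and 5–30%. The affected events range from 214 × 0.10 × 0.05 ≈ 1 to 214 × 0.30 × 0.30 ≈ 19. Simulation used 500 trials per scenario, 262 subjects, exponential PFS with medians 4.5 and 7.0 months, 20 months of accrual and 26 months in total. The last column is the shift in the median observed time, not the Kaplan-Meier median.

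| PFS events that are deaths | Day missing | HR ratio, imputed / true | Shift in median, control / investigational (months) |
|---|---|---|---|
| 10% | 5%, both arms | 1.0000 | −0.004 / −0.002 |
| 20% | 10%, both arms | 1.0001 | −0.010 / −0.005 |
| 30% | 30%, both arms | 1.0003 | −0.043 / −0.032 |
| 30% | 30%, control only | 0.9944 | −0.043 / 0 |
| 30% | 30%, investigational only | 1.0055 | 0 / −0.027 |

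The simulation moves dates only. It does not model changes of event status through the censoring rules.

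**With a floor.** Taking the later of the first of the month and the day after the last date known alive removes the orders in which death precedes a record of life. The mean early shift falls from 14.7 days to 10.7 (G = 42), 12.0 (G = 61) or 12.7 (G = 84). The 15th with the same floor leaves a mean error of about 0 to 0.4 days.

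**The case against.** The best defence is that the rule will rarely fire for PFS and hardly matters when it does. Deaths during treatment or safety follow-up fall under SAE reporting: notice within 24 hours, with onset time and outcome (Protocol 13.2.5), and deaths from progression are included (13.2.3). CRF items may not be left blank (15.1.2). Survival contacts start only after safety follow-up, by which time many subjects will have progressed or been censored under SAP 4.1.1.1. The rule is also the same in both arms. All of this stands, and it limits the size of the point. It does not justify a rule that, when it fires, can contradict recorded dates.

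Three stronger readings are tempting, and the documents do not support them.

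- A reader might infer that partial death dates are likely because sites learn of deaths by phone every 2 months. That contact schedule belongs mostly to the period after PFS is settled, and no document gives a count.
- A reader might infer that both PFS and OS are shortened. PFS is affected only where the imputed death becomes the event or alters the censoring order. OS is not analysed in this SAP.
- A reader might infer a biased treatment comparison. Earlier event times in both arms are not a biased hazard ratio, and the simulation shows almost no movement when missingness is similar.

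One caution remains. After the last dose the investigational arm is contacted at days 30, 60 and 90, while control subjects who do not cross over have one visit at day 21 and then 2-monthly contacts. Equally complete death dates in both arms are therefore not assured.

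**Conclusion.** The rule is defective as written but minor in effect. Applied literally, it can date a death before evidence of life or before randomization, and it can alter which PFS censoring rule applies. Its error is never in the late direction and averages about 14.5 days. The 35%, 18% and 24% figures hold only for deaths with a missing day and rest on a uniform gap from last scan or contact to death.

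Under the assumed ranges the hazard ratio changes by less than 0.1% with equal missingness, and by about 0.6% if 30% of days are missing in one arm only. The conclusion does not extend to OS unless the Protocol's OS endpoint is analysed with the same date rule.

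**What to change.** In SAP 5.1.4, impute a missing day of death as the later of the first day of the month of death and the day after the last date known alive (last scan, visit or contact). Let that date also take in randomization and the start of any new anti-tumor drug, so that those orders are protected too. A missed scan is not evidence of life, so the floor does not fully settle the missed-scan order.

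Optionally, add a sensitivity analysis that uses the 15th with the same floor, because the floor alone removes impossible orders but not all of the early shift.

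Do not add a rule that censors a known death when the month is also missing. It would discard a PFS event, and censoring at last contact would conflict with SAP 4.1.1.1, which censors at the last tumor evaluation.

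The cost is one sentence, or two with the sensitivity analysis. No new data are needed, and the 214 events and 292 subjects stay as they are. SAP section 1 describes this as an initial version to be finalised before database lock, so the change can be made then.
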